APPENDIX IV: INFORMED CONSENT FORM

The study template informed consent form is available under a separate cover.

Clinical Investigation Plan

APPENDIX V: MONITORING PLAN

A copy of the Monitoring Plan can be obtained upon request from the Sponsor Clinical Project Manager.

Clinical Investigation Plan

APPENDIX VI: DEVICE POSITION SUBSTUDY PROTOCOL

Study Title	Assessment of HeartMate 3 Device Position using a Radiopaque Marker Positioned on the Aortic Root
Study Phase	Substudy within the ARIES Clinical Study
Rationale	
Implantation of a durable left ventricular assist device (LVAD) is now the most frequently utilized surgical therapy for treatment of patients with advanced heart failure (HF) refractory to medical management. Previous studies have demonstrated that inflow cannula malposition, which occurs 1) due to incorrect surgical placement, or 2) as a consequence of device migration, is associated with significant adverse events including pump thrombosis, stroke and persistent heart failure due to the inability to provide adequate left ventricular unloading and device flow.⁽¹⁾
 
Specific surgical configurations have not been studied in depth, and its influence on hemocompatibility-related events associated with LVAD therapy remains poorly understood.⁽²⁾ Thrombogenesis in patients with an LVAD is at least, in part, attributable to nonphysiological blood flow characteristics: shear environments, as well as high spatial gradients and high-frequency temporal fluctuations, which lead to platelet activation. This adverse hemodynamic environment may be exacerbated by malposition of the LVAD inflow cannula. Anecdotal evidence suggests that surgical implantation of the inflow cannula at different angles with respect to the apical ventricular axis influences LVAD thrombosis.⁽³⁻⁵⁾
 
Prior studies investigating inflow cannula malposition have utilized various reference lines to determine optimal inflow cannula position. Typically, these reference lines utilize the spine as a vertical reference line and a horizontal line drawn perpendicular to the vertical line usually positioned at the apex of the right diaphragm serves as a horizontal reference point.⁽³⁻⁵⁾ However, this approach does not take into consideration differences in anatomy of the heart in relation to the spine and diaphragms. Optimal inflow position is oriented to the orifice of the mitral valve. Thus, the utility of these reference lines to identify the orifice of the mitral valve is brought into question.
 
This substudy utilizes a simple technique to identify a more anatomical reference point to assess HeartMate 3 inflow cannula position. A radiopaque surgical marker (i.e., surgical clip) will be placed on the anterior surface of the aortic root below the sino-tubular ridge of the aorta just above the ostia of the right coronary artery.
 
The surgical clips used in this study are generally standard to use in cardiac surgery for both hemostasis and as radiopaque markers. They have been used for the development of this substudy in 4 LVAD implants with a cumulative follow up of 245-days post-implant at a single center without safety concerns (data not published). The location of the clip reduces the likelihood of interference with the coronary artery. Placement of the clips will be under direct visualization and will not prolong the implant procedure. Participation in this substudy is not expected to present appreciable additional risk. This substudy will not affect the main objectives of the ARIES HM3 clinical trial.


Clinical Investigation Plan

[figure not shown]
	
The hypothesis of this sub-study is to develop and validate a surgical marker to serve as a consistent anatomical landmark to allow for accurate evaluation of the HeartMate 3 inflow canula position at the time of implant and subsequently, over time. We further hypothesize that differences in inflow canula positions and their changes over time may correlate with clinical outcomes.

Primary Objectives	
To develop and validate the use of a radiopaque surgical marker placed on the anterior surface of the aortic root below the sino-tubular ridge of the aorta just above the ostia of the right coronary artery to be used as a surrogate anatomical reference or landmark to more optimally assess HeartMate 3 inflow cannula position. Validation will be performed by assessing:
 
 1. The safety and feasibility of placing and visualizing the radiopaque marker; 2. The variation in cannula angulation relative to the radiopaque marker and cannula positional changes over time; 3. The relationship between the initial cannula angulation or its change over time with adverse clinical outcomes and functional capacity, as an exploratory analysis.
Study Populations	Subjects enrolled in the ARIES HM3 study who also meet eligibility requirements for this substudy at participating centers.
Study Design	Multi-center, prospective, non-controlled, non-randomized, observational sub-study within ARIES
Number of Subjects	Per ARIES HM3 study
Number of Centers	Up to 10 Centers
Duration of Subject Participation	Per ARIES HM3 study
Inclusion Criteria	
 1. Subjects enrolled within the ARIES HM3 study.
Exclusion Criteria	
 1. In the judgement of the implanting surgeon, that placement of the radiopaque surgical marker would have unacceptable risk based upon technical reasons or patient anatomy. 2. Subjects undergoing placement of the HeartMate 3 device through a minimally-invasive approach where sternotomy or upper sternotomy will not be performed and access to the anterior surface of the aorta below the sino-tubular ridge is not feasible.

Clinical Investigation Plan

Intervention	A radiopaque surgical marker (i.e., surgical clip) will be placed on the anterior surface of the aortic root midway between the sino-tubular ridge of the aorta and the ostia of the right coronary artery. The radiopaque marker will include placement of 2 standard surgical clips (manufacturer, size, picture; see Figures 1, 2A and B, 3 and 4) attached to the adventitia of the aorta and positioned as described above.
Assessments	Anteroposterior (AP) and lateral radiographs will be captured prior to discharge (but within 30 days of implant) and at the 3-month follow up visit. Radiographs will be obtained by a fixed radiography (fixed x-ray) and sent to the study sponsor in DICOM format. If standard of care (SOC), chest x-ray computed tomography (CT) scans will be obtained in addition to the radiographs.
References	

[figure not shown]
Clinical Investigation Plan

Figure 1: Acceptable Anteroposterior and Lateral Chest Radiograph Demonstrating Placement of a Radiopaque marker (two standard surgical clips). Clips are placed on the anterior surface of the aorta positioned halfway between the sino-tubular ridge of the aorta and the right coronary artery. Note: the full body of the HM3 is visible within the radiograph.

[figure not shown]
Clinical Investigation Plan

Figure 2A: Measurement Method on Anteroposterior and Lateral Chest Radiograph. Radiopaque marker (two standard surgical clips) on the anterior surface of the aorta is positioned halfway between the sino-tubular ridge of the aorta and the right coronary artery (Red Arrow). Black line indicates center line of the HeartMate 3 inflow canula. The dotted red line indicates the degree of deviation from the reference point (surgical radiopaque marker).

Clinical Investigation Plan

Figure 2B: Measurement Method on Anteroposterior and Lateral Chest Radiograph. Radiopaque marker (two standard surgical clips) on the anterior surface of the aorta is positioned halfway between the sino-tubular ridge of the aorta and the right coronary artery (Red Circle). Black line indicates center line of the HeartMate 3 inflow canula. The dotted red line indicates the degree of deviation from the reference point (surgical radiopaque marker).

Clinical Investigation Plan

Figure 3: Radiopaque Surgical Marker

Clinical Investigation Plan

Figure 4: Radiopaque Surgical Marker

Clinical Investigation Plan

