5.0 SUBJECT SELECTION AND WITHDRAWAL

5.1 Subject Population

This clinical investigation will enroll male and female subjects from the advanced heart failure population who, as part of their standard course of treatment, will receive a HM3 LVAD. Subjects are considered enrolled when they provide written informed consent. Subjects must meet all applicable eligibility criteria and provide written informed consent prior to the conduct of any investigation-specific procedures not considered standard of care. Furthermore, patients must meet all randomization eligibility requirements at randomization. Only randomized subjects will continue to be followed in this study. Subjects not meeting randomization eligibility requirements will be considered screen failures and withdrawn from the study. Reason(s) for not meeting randomization eligibility requirements will be captured in the study EDC. Randomized subjects ongoing without a surgical adverse event, defined as ≤ 14 days post-implant, requiring investigator mandated antiplatelet therapy will form the analysis population for study endpoints. Details are available in section 8 of this CIP and the SAP.

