5.5 Subject Withdrawal

If a subject does not meet all inclusion criteria, or meets at least one exclusion criteria after the subject is enrolled (consented), but prior to randomization, the subject will be considered a screen failure and withdrawn and will not be included in the analysis populations.

Those enrolled (consented) subjects that meet all inclusion criteria and no exclusion criteria post implant will be randomized within 2-7 days post-implant (the day of implant is day 0). However, if these subjects do not meet the randomization eligibility criteria, are not randomized, never start the treatment arm regimen, experience a surgical event (≤ 14 days post implant) that requires investigator mandated anti-platelet therapy or experience an outcome ≤ 14 days post implant then they will be withdrawn.

Each randomized subject shall remain in the clinical investigation until completion of the required follow-up period; however, a subject's participation in any clinical investigation is voluntary and the subject has the right to withdraw at any time without penalty or loss of benefit. Conceivable reasons for discontinuation may include, but not be limited to, the following:

- Subject outcome including death, transplant, or device explant or exchange
- Physician or subject voluntary withdrawal
- Subject lost-to follow-up as described below.

The Sponsor must be notified of the reason(s) for subject discontinuation. The site will provide this information to the Sponsor. Investigators must also report this to their respective IRB/EC as defined by their institution's procedure(s).

No additional follow-up will be required or data recorded from subjects once withdrawn from the clinical investigation, except for the reason and status at the time of withdrawal (deceased/alive). Subjects withdrawn from the study will cease treatment arm medication and be transitioned to an anticoagulation regimen in accordance with site standard of care by the investigator.

In case of subject withdrawal of consent, the site should make attempts to schedule the subject for a final clinical investigation visit. At this final follow-up visit, the following will be recorded, with the subject's permission:

- Subject status (deceased/alive)
- Any adverse event details prior to withdrawal of consent

Lost-to-Follow-up

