APPENDIX B: Device Position Substudy

A substudy is proposed to develop and validate the use of a radiopaque surgical marker placed on the anterior surface of the aortic root below the sino-tubular ridge of the aorta just above the ostia of the right coronary artery to be used as a surrogate anatomical reference or landmark to more optimally assess HeartMate 3 inflow cannula position. The substudy will include subjects enrolled in the ARIES HM3 study who also meet eligibility requirements for this substudy at participating centers. Validation will be performed by assessing:

1. Safety and feasibility assessment of the radiopaque surgical marker will be made using anteroposterior (AP) and lateral radiographs captured prior to discharge (but within 30 days of implant) and at the 3-month follow up visit. The following assessments will be descriptively presented as the number and percentage of subjects for each category: successful placements, successful visualizations, and gross migrations. Adverse events related to the clip or placement procedure will be presented as the number and percentage of subjects enrolled in the substudy and total number of events.
2. The angular position of the canula relative to the marker will be measured from the AP view, and the distance of the marker to the axial alignment of the canula will be measured from the lateral view. The cannula position relative to the radiopaque marker and cannula positional changes over time will be descriptively and graphically summarized from both the AP and lateral radiographs. These measurements will be summarized as mean with standard deviation, and by quartiles, minimum and maximum values.

The radiographs recorded at both pre-discharge and 3 months will be reviewed by an independent evaluator and assessed visually for cannula position at both time points along with potential significant change in position from pre-discharge to 3 months. Visual assessments will be categorized and summarized as count and percentage of subjects enrolled in the substudy.

3. Patients may also be grouped into clusters with each cluster representing different levels of change in cannula position. Comparisons of adverse clinical outcomes and functional capacity including the following will be made between clusters:
 - Adverse Events: Mortality, Stroke, Pump Thrombosis, Bleeding, Major HRAE, HRAE, Right Heart Failure, Cardiac Arrhythmia
 - Major thrombotic and major hemorrhagic events
 - Hospitalizations

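### The device-position substudy loses clipped subjects who are withdrawn after implant but keeps them in the SAP denominator, so later clip events and 3-month position change are understated

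*Protocol*

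**What the plan says.** Appendix VI of the protocol draws the substudy population from the main trial: "Subjects enrolled in the ARIES HM3 study who also meet eligibility requirements for this substudy at participating centers". Section 5.1 fixes what enrolment means: "Subjects are considered enrolled when they provide written informed consent". The marker goes on at surgery: "Placement of the clips will be under direct visualization and will not prolong the implant procedure".

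Randomisation comes later, on days 2 to 7 (protocol Section 5.5). Subjects found ineligible by then are screen failures (Section 5.3). Section 5.5 also withdraws subjects who never start study medication, have a surgical event by day 14 that leads to mandated antiplatelet therapy, or reach an outcome by day 14. Section 5.1 adds: "Only randomized subjects will continue to be followed in this study". Section 5.5 states the consequence: "No additional follow-up will be required or data recorded from subjects once withdrawn from the clinical investigation", apart from the reason for withdrawal and vital status.

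The substudy films are due before discharge (within 30 days of implant) and at 3 months. Participation lasts as long as in the main study, and Appendix VI makes no exception for clipped subjects who are withdrawn.

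SAP Appendix B gives the safety denominator: "Adverse events related to the clip or placement procedure will be presented as the number and percentage of subjects enrolled in the substudy". It uses the same denominator for the independent evaluator's visual assessment of cannula position and change. For placement, visualisation and gross migration it asks for a number and percentage of subjects, without saying which subjects or how a missing film counts.

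Appendix VI also excludes a subject when the implanting surgeon judges that "placement of the radiopaque surgical marker would have unacceptable risk based upon technical reasons or patient anatomy".

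**The concern.** The substudy's first objective is to show that the marker is safe and feasible to place and see. Appendix VI reports that the technique's development covered 4 implants and 245 cumulative days of follow-up at one centre, so this substudy has to supply most of the evidence.

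The clip is in place before the main trial decides whether it will keep the subject. Someone clipped on day 0 who then needs additional circulatory support, stays nil by mouth through day 7, or has antiplatelet therapy mandated or ruled out is withdrawn. That subject has no required 3-month film, and no pre-discharge film if it had not yet been taken. A clip problem arising after withdrawal is not collected. The SAP nevertheless leaves the subject in the denominator for clip events and visual position. Some subjects would also carry a study-placed marker without study safety follow-up.

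**Working it through.** **1. Figure to reproduce.** There is none. Appendix VI gives the number of subjects only by reference to the main study, and neither document states an expected rate, precision target or success threshold for the substudy. The rates below are assumptions that show direction and rough size.

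**2. The order of events.**

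| Time | What happens | Source |
|---|---|---|
| Consent | Enrolled; safety reporting starts | Protocol 5.1, 7.3.1 |
| Day 0 | Clip placed at implant | Appendix VI |
| Days 2-7 | Randomised, or screen failure and withdrawn | Protocol 5.3, 5.5 |
| To day 14 | Withdrawn for a qualifying surgical event or an outcome | Protocol 5.4, 5.5 |
| Before discharge, within 30 days | First film | Appendix VI |
| Month 3 | Second film | Appendix VI |

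Both films can fall after withdrawal, and the second always does.

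**3. Clip-related adverse events.** Let w be the share of clipped subjects withdrawn, a_r and a_w the event rates in retained and withdrawn subjects, and c the share of withdrawn subjects' events recorded before they leave.

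- True rate = (1 − w)·a_r + w·a_w
- Reported rate, enrolled denominator = (1 − w)·a_r + w·a_w·c

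The shortfall is w·a_w·(1 − c), which is never negative. It is zero only if every event in withdrawn subjects occurs and is recorded before withdrawal (or none occur).

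Events arising only after withdrawal would occur (c = 0), a_r = a_w = 2%:
- w = 5%: 0.95 × 2% = 1.9%
- w = 15%: 0.85 × 2% = 1.7%
- w = 30%: 0.70 × 2% = 1.4%

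Higher rate in withdrawn subjects (a_r = 2%, a_w = 6%, w = 15%): true rate 0.85 × 2% + 0.15 × 6% = 2.6%. Reported: 1.7% if c = 0; 1.7% + 0.45% = 2.15% if c = 0.5; 2.6% if c = 1.

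**4. Visual position change.** This needs both films. If a share q truly changes and withdrawn subjects have no second film, the reported share is (1 − w)·q when change is equally common in both groups. That is 0.95, 0.85 or 0.70 of the true share for w = 5%, 15% or 30%.

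**5. Visualisation.** Assume 95% visible in retained subjects and 80% in withdrawn ones.

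| w | All clipped (true) | Retained only | Enrolled, missing counted as not visible |
|---|---|---|---|
| 5% | 94.25% | 95.0% | 90.25% |
| 15% | 92.75% | 95.0% | 80.75% |
| 30% | 90.5% | 95.0% | 66.5% |

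For w = 15%: true = 0.85 × 95% + 0.15 × 80% = 92.75%; last column = 0.85 × 95% = 80.75%. One convention errs upward and the other downward. If visibility is equal in both groups, retained-only is unbiased. The SAP does not choose between them, so the direction cannot be known. The same gap affects gross migration.

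**6. Placement.** The result is known at surgery, so later withdrawal does not distort it if all attempts are counted. If the surgeon excludes 5% to 20% of those considered and 95% of attempts succeed, success among all considered is 0.95 × 95% = 90.25% down to 0.80 × 95% = 76.0%. These answer a different question from the 95% among eligible subjects.

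**The case against.** The strongest reply has four parts.

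- **Early events are captured.** Protocol Section 7.3.1 starts safety reporting at consent and records events that disqualify a subject from randomisation. Placement complications would be expected at or soon after surgery. This stands, and it limits the size: the shortfall concerns events after withdrawal only.
- **The SAP uses enrolled loosely.** SAP Section 2.10 reports events in the analysis populations as a percentage of all enrolled, although SAP Section 2.1 requires randomisation for those populations. Appendix B might therefore mean retained subjects. That reading does not rescue the figure. It removes the dilution but drops early events in clipped subjects who were withdrawn, giving 2.0% instead of 2.6% in the second example of step 3.
- **The surgeon's exclusion is a declared safety criterion.** This stands. A reader might infer that placement success is close to 100% by construction. The documents do not support that: a prior judgement of risk does not guarantee success, and visualisation and migration are reported separately. The criterion narrows the population described, and the percentage within that population is not wrong.
- **The substudy is descriptive.** It is observational, has no success threshold, uses clips that Appendix VI calls generally standard in cardiac surgery, and is stated not to affect the main objectives. This stands and keeps severity low.

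A reader might also infer that the subjects lost are the sickest or those with early bleeding. The documents do not show this. The exclusion for mandated antiplatelet therapy concerns other conditions, and nothing ties the reasons for withdrawal to clip visibility or clip events.

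**Conclusion.** The point holds for two measures. Under the stated denominator, clip events after withdrawal and position change at 3 months can only be understated. If both are equally common in withdrawn and retained subjects, the relative loss equals the share of clipped subjects withdrawn, which the documents do not give. At the assumed 5% to 30%, an assumed 2% later event rate loses 0.1 to 0.6 percentage points. Events recorded before withdrawal reduce the loss. Clipped subjects who died by day 14 could not have had later events, so w should be read as those alive with the clip in place.

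A reader might conclude that all the safety and feasibility percentages come out too favourable. The documents do not support that. Visualisation and migration can err either way because the SAP states neither denominator nor missing-film rule, and the surgeon's exclusion is a limit on generalisability. Severity is low: nothing here reaches the main trial's primary endpoint.

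**What to change.** 1. **Clip adverse events (SAP Appendix B).** Report placement-related and early clip events over all subjects in whom a clip was attempted or placed, including those later withdrawn. Report later clip events over clipped subjects still under follow-up, or per time at risk. Early events must not disappear because the subject was withdrawn.
2. **Film-based results (SAP Appendix B).** Report visualisation, migration and visual position over clipped subjects with the film or films required. Beside them give the number clipped, the number withdrawn before imaging, and bounds that count all missing films as failures and then as successes. In the 15% example of step 5 the bounds for visualisation are 80.75% and 80.75% + 15% = 95.75%.
3. **Placement (SAP Appendix B).** Next to as-attempted success, show how many placements were not attempted because of the surgeon's exclusion, with reasons. The surgeon's discretion is unchanged.
4. **Follow-up (protocol Sections 5.1 and 5.5, and Appendix VI).** Add an exception so that, with consent, clip-related adverse events and any radiographs taken are collected through 3 months in clipped subjects who are not randomised. Appendix wording alone would conflict with the two main sections.

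Items 1 to 3 change reporting only. Item 4 costs a protocol amendment and limited extra data collection in a few subjects. If the sponsor declines item 4, items 1 to 3 still make the loss visible, but later clip events in withdrawn subjects stay unknown.
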